430         title'Calculate CIs and P values';
431     run;
432
433     Datasets used: MASKEDEXAMS, ROSTER
```

434 **Objective #3: Compare 3-year stereoacuity between BLR and R/R treatment groups**

- 435 1. Limit the analysis to patients who completed the 3-year visit.
436 2. Define the outcomes as distance stereoacuity and near stereoacuity.
437 3. Create change in stereoacuity between baseline and 3 years.
438 4. Obtain distribution of 3-year stereo and change in 3-year stereo.
439 5. Compare mean 3-year outcomes between treatment groups adjusting for corresponding baseline
440 stereoacuity.

441 **Technical Plan**
442

- 443 1. Limit the analysis to patients who completed the 3-year visit. Use the 3-year visit data for all patients
444 who completed the 3-year visit, regardless of what treatment(s) were received or if the patient had
445 undergone reoperation.
446 2. Define outcomes as distance and near stereoacuity, using existing log scale stereoacuity.
447
448 3. Create change in stereoacuity as the baseline value minus the 3-year value, so positive values =
449 improvement.
450
451 4. Run proc means to obtain distribution of 3-year stereo and change in 3-year stereo.
452
453 5. Compare mean 3-year outcome between treatment groups using ANCOVA model adjusting for
454 corresponding baseline stereoacuity.
455

456 `proc genmod data = roster;`
457 `class trtgroup;`
458 `model stereodi_36 = trtgroup stereodi_0;`
459 `where comp_36 = 1;`
460 `title1'Comparison of 3-year distance stereoacuity between treatment groups';`
461 `run;`
462

463 **Datasets used: ROSTER**
464

465 **Objective #4: Compare complete or near-complete resolution at 3 years between BLR and R/R**
466 **treatment groups**

- 467 1. Define complete or near-complete resolution outcomes:
- 468 • Complete or near-complete resolution at 3 years without regard to previous failure (post hoc)
 - 469 • Complete or near-complete resolution at 3 years with no previous failure (consistent with pre-
 - 470 specified “success” criteria in the protocol).
- 471
- 472 2. Calculate complete or near-complete resolution outcomes using 3-year alignment, 3-year
- 473 stereoacuity, nonsurgical treatment for IXT during the study, reoperation data. In addition,
- 474 suboptimal surgical outcome **by** 3 years will also be used to calculate complete or near-complete
- 475 resolution AT 3 years with no previous failure.
- 476
- 477 3. For each definition, compare proportion of participants with complete or near-complete resolution
- 478 at 3 years between treatment groups and calculate 95% CI.
- 479

480 **Technical Plan**

- 481
- 482 1. Complete or near-complete resolution AT 3 years without regard to previous failure (post hoc)
- 483 was defined as meeting all of the following at the 3-year visit:
- 484
- 485 1. Exodeviation <10 PD (tropia or phoria) by both SPCT and PACT at distance and near and
 - 486 either ≥ 10 PD reduction in 3-year PACT magnitude from both the distance and near
 - 487 preoperative* angles ≥ 10 PD if the corresponding preoperative angle was ≥ 10 PD, or reduction
 - 488 to orthodeviation by PACT if corresponding preoperative angle was <10PD. *Because all*
 - 489 *patients in the basic primary cohort had distance and near PACT ≥ 10 PD, the last phrase was*
 - 490 *not applicable and therefore not included in the definition in the manuscript.*
 - 491 2. Esotropia <6 PD at distance and near by SPCT
 - 492 3. No decrease in Preschool Randot of ≥ 2 octaves from enrollment stereoacuity or to nil
 - 493 4. No reoperation or treatment with botulinum toxin
 - 494 5. No non-surgical treatment for a recurrent or residual exodeviation (nonsurgical treatment for
 - 495 esodeviation was allowed)

496 **Preoperative angle represents the largest deviation by PACT at distance, near, and remote*

497 *distance at the enrollment visit if no additional preoperative (pre-randomization), PACT*

498 *measurements were taken closer to the surgery date; OR the PACT deviation entered on the*

499 *randomization form if any additional preoperative PACT measurements were taken closer to the*

500 *surgery date.*

- 501
- 502 Complete or near-complete resolution AT 3 years with no previous failure was defined as follows:
- 503 • Patients who had suboptimal surgical outcome at any time will be considered not resolved
 - 504 • All other patients will have same values as for complete or near-complete resolution AT 3
 - 505 years without regard to previous failure.
- 506

- 507
508
2. Calculate complete or near-complete resolution outcomes using baseline alignment (see note), 3-year alignment, 3-year stereoacuity, nonsurgical treatment for IXT during the study, reoperation

509
510

data. In addition, suboptimal surgical outcome **by** 3 years will also be used to calculate complete or near-complete resolution AT 3 years with no previous failure.

511 • Note for baseline alignment for calculating whether distance and near angles have had the
512 requisite reduction in PACT: In addition to distance and near PACT which were measured at
513 enrollment, one or more PACT angles may have been re-measured closer to (but before)
514 randomization. The single PACT measurement that was entered on the randomization form
515 was the largest recorded at near, distance, or remote distance fixation, and was the angle upon
516 which surgical dose would be based--and may have been one of the enrollment angles or an
517 angle measured closer to (but before) randomization. If the angle entered on the
518 randomization form was measured at remote distance, the enrollment distance and near were
519 used for the baseline alignment; if the angle entered was measured at distance or near, then this
520 angle was used for the corresponding baseline measurement and the enrollment data used for
521 the remaining measurement.

522

523 3. For each outcome, compare the proportion of participants with complete or near-complete
524 resolution using Barnard's exact test and specifying the FMSCORE option to obtain 95%
525 confidence intervals from Farrington-Manning score.

526

```
527 proc freq data = roster;  
528     tables trtgroup*compresolve / nocol nopercnt;  
529     exact barnard riskdiff (method=fmscore);  
530     where comp_36 = 1;  
531     title1 "Comparison of Complete or Near-complete Resolution Without Regard to  
532 Previous Failure";  
533 run;
```

534

535 **Datasets used: ROSTER**

536

537

Objective #5: Compare 3-Year IXT Questionnaire (IXTQ) Scores Between Treatment Groups

538

1. Obtain IXTQ data from existing verified SAS dataset **IXTQ.IXTQALL_19OCT2017** provided by [name]. Include the following:

539

540

- a. **Rasch score for each component IXTQ (or parent subscale)**

541

- b. **0 to 100 score for each component IXTQ (or parent subscale)**

542

2. Test ANOVA assumptions for normality, homogeneity of variance.

543

3. Test ANCOVA assumption of homogeneity of slopes for parent and proxy only (child versions using ANOVA).

544

545

4. For older and younger child IXTQ, parent proxy IXTQ, and for each of parent subscales between compare distribution Rasch proxy score between treatment groups.

546

547

5. List median 0 to 100 score (based on Rasch score) for each treatment group.

548

549

Technical Plan

550

1. Use SAS IXTQ dataset **IXTQ.IXTQALL_19OCT2017** provided by [name]

551

```
*IXT1 IXTQ;
```

552

```
libname IXTQ 'F:\user\PEDIG\Manuscripts-
```

553

```
Presentations\Manuscripts\IXT\IXT2\IXTQ\Manuscript Analysis\Datasets';
```

554

- Contains one record per IXTQ completed at enrollment and 3 years for both IXT1 and IXT2 studies.

555

556

- Take enrollment and 3-year questionnaire scores for IXT1 patients from **IXTQ.IXTQALL_19OCT2017** and add to ROSTER dataset.

557

558

- Scores are also included as follows:

559

- a. For the child IXTQ component, 5 to 7 year version scores are include for children aged 5 to 7 at the time of testing; 8 year and older version scores are include for children aged 8 or older at the time of testing; no child component scores are included for children younger than 5 years at the time of the visit. The variable AGE indicates the child's age at the time of testing.

560

561

562

563

564

- b. For the parent proxy IXTQ component

565

- c. For the parent IXTQ component: each of the three parent IXTQ subscales of psychosocial, function, and surgery.

566

567

- For each IXTQ component or subscale, a Rasch-based score and a 0 to 100 score (based on Rasch score) are included.

568

569

- Note that some participants were too young for the IXTQ at baseline (those enrolled 3-<5 years of age) but completed the 5 to 7 year old IXTQ version at interim visits and at the 3-year visit once the child turned 5 years old. Also note that some children completed the 5 to 7 year old IXTQ version at baseline and the 8 years and older version at 3 years.

570

571

572

573

574

2. Test ANOVA/ANCOVA assumptions for normality, homogeneity of variance, and homogeneity of slopes.

575

576

- Test for normality using Shapiro-Wilkes test

576

```
577 %macro normalitytest (outcome);  
578 %sort (roster, trtgroup);  
579 proc univariate data = roster normal;
```

```

580         var &outcome;
581         by trtgroup;
582     run;
583     %mend;
584

```

```

585     %normalitytest (ParentPsychRaschMean_36);
586     /* Note that all look non-normal(Shapiro-Wilkes test P values all < 0.05 */

```

- Test for homogeneity of variance using Levene's test

```

588     %macro variancetest (outcome);
589     proc glm data = roster;
590         class trtgroup;
591         model &outcome = trtgroup;
592         means trtgroup / hovtest=levене(type=abs) hovtest=bf;
593         title1"ASSESSING ASSUMPTION OF EQUALITY OF VARIANCES FOR '&OUTCOME'";
594     run;
595     quit;
596     %mend;
597
598     %variancetest (ParentPsychRaschMean_36);
599

```

```

600     /* Note that all look OK except for child younger -- not equal */

```

- Test for homogeneity of regression slopes using regression model with interaction term

```

602     %macro slopetest (outcome, predictor);
603     proc glm data = roster;
604         class trtgroup;
605         model &outcome = trtgroup &predictor trtgroup*&predictor;
606         title1"ASSESSING ASSUMPTION OF EQUALITY OF SLOPES FOR '&OUTCOME' BY INCLUDING
607         INTERACTION TERM IN THE ANCOVA MODEL";
608     run;
609     %mend;
610
611     %slopetest (ParentPsychRaschMean_36, ParentPsychRaschMean_0);
612
613     /* all look OK */
614

```

- 615
3. For each of the two age-specific child IXTQs, the IXTQ proxy questionnaire, and for each of the three parent questionnaire subscales (psychosocial, functional, and surgical), compare distribution of Rasch-based QOL scores at 3 years using Wilcoxon Rank Sum test.

```

616
617
618
619
620     %macro wilcoxon (outcome);
621     proc npariway data = roster plots=none wilcoxon;
622         class trtgroup;
623         var &outcome;
624         title1"NONPARAMETRIC WILCOXON RANK SUM COMPARING '&OUTCOME' BETWEEN TREATMENT
625     GROUPS";
626     run;
627     %mend;
628
629     %wilcoxon (ProxyRaschMean_36);
630

```

- 631 4. Since all analyses have at least one assumption violated, switch to using non-parametric Wilcoxon
632 rank sum test to compare distributions between treatment group, instead of means using ANOVA
633 or ANCOVA.
- 634
- 635 5. Calculate median of median 0 to 100 score at 3 years using proc means.
636

637 **References**

638 ¹Leske DA, Holmes JM, Melia M, on behalf of Pediatric Eye Disease Investigator Group. Evaluation of
639 the Intermittent Exotropia Questionnaire using Rasch analysis. *JAMA Ophthalmol* 2015;133:461-5.

640 ²Leske DA, Hatt SR, Liebermann L, Holmes JM. Evaluation of the Adult Strabismus-20 (AS-20)
641 Questionnaire Using Rasch Analysis. *Invest Ophthalmol Vis Sci* 2012.

642 ³Leske DA, Hatt SR, Liebermann L, Holmes JM. Lookup Tables Versus Stacked Rasch Analysis in
643 Comparing Pre- and Postintervention Adult Strabismus-20 Data. *Transl Vis Sci Technol* 2016;5:11.
644

645 **Datasets used: ROSTER, IXTQALL_19OCT2017**
646

647 **Objective #6: Tabulate non-surgical treatment prescribed for BLR and R/R treatment groups**
648 **separately**

649 **1. Define nonsurgical treatment of interest as that which was prescribed for XT, ET, or**
650 **diplopia.**

651 Because the reason for this nonsurgical treatment was not specified other than being prescribed for
652 XT, ET, or diplopia, the type of deviation that was present when the nonsurgical treatment was
653 prescribed was reported. This data was used to report the proportions of participants with non-
654 surgical treatment prescribed when exodeviation was present, when esodeviation was present, and
655 when exodeviation and esodeviations were present at different times during the study. Among
656 participants who met the constant esotropia suboptimal surgical outcome during the study, the
657 proportion who had nonsurgical treatment prescribed was reported.

658
659 Do not include nonsurgical treatment prescribed for amblyopia, which was recorded in a different
660 section of the data form.

661
662 **2. Obtain alignment data**

663
664 **3. Create patient level flag variables for the following:**

- 665 • Nonsurgical treatment when XT is present anytime during study
- 666 • Nonsurgical treatment when ET is present anytime during study
- 667 • Non-surgical treatment when XT and ET are present (different times during study)

668 **Technical Plan**

669 **1. Get treatment prescribed records from the SQL data table TBLIXT1TREATRX. Obtain**
670 **visit date from the login table.**

671 Use: NonSurgTmtRxNone, NonSurgTmtRxPrism, NonSurgTmtRxPatch,
672 NonSurgTmtRxOverMinus, NonSurgTmtRxVT, NonSurgTmtRxOther, NonSurgTmtRxOtherDs

673
674 Do not use: AmbTrtRxNone, AmbTrtRxPatch, AmbTrtRxAtrp, AmbTrtRxVT,
675 AmbTrtRxOverPlus, AmbTrtRxBang, AmbTrtRxOther, AmbTrtRxOtherDs

676
677 **2. Obtain SPCT and PACT alignment data for maskedexams from verified dataset**
678 **MASKEDEXAMS. Obtain similar data from the 1 week and 8 week visits from the SQL**
679 **data table TBLIXT1OCUALIGN.**

680
681 Consider XT present if exotropia is present by SPCT or exodeviation is present by PACT
682 Consider ET present if esotropia is present by SPCT or esodeviation is present by PACT

683
684 Merge alignment data into treatment prescribed records.

685
686 **3. Create patient level flag variables for the following:**

687

- Nonsurgical treatment when XT is present anytime during study

688

- Nonsurgical treatment when ET is present anytime during study

689

- Non-surgical treatment when XT and ET are present (different times during study)

690

691

692

693

694

695

1. Loop through the treatment prescribed records, retaining flags for non-surgical treatment when XT is present and for non-surgical treatment when ET is present.
2. Take last record for each patient.
3. Add flags to roster dataset.
4. Create flag for non-surgical treatment when XT and ET using XT and ET treatment flags .

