267 The proposed changes are to make refractive error eligibility and prescription guidelines
268 consistent with those in the IXT2 study. The reasons for this change are as follows: 1) it was felt
269 that making these items parallel between the two studies will avoid confusion among study
270 investigators, 2) it is expected that the percentage of otherwise-eligible IXT patients with
271 hyperopia greater than +3.50 D SE is very low, and 3) that patients with very high hyperopia
272 might be more likely to have a neurologic condition and might be a different than the typical IXT
273 patient

274

275 **Protocol Change #3**

276

277 Current Protocol

278 All patients are randomized regardless of whether the magnitude of their exodeviation increased or
279 decreased out of study eligibility range (15 to 50 PD) before surgery has occurred.

280

281 Proposed Change

282 Patients in whom the magnitude of the largest of the most recent distance, near, and remote
283 distance angles has decreased to <15 PD or increased to >50 PD before surgery will be dropped
284 from the study if they have not yet been randomized. If such patients have already been
285 randomized, it is at investigator discretion whether to perform surgery and what type of surgical
286 method to perform (i.e. BLRrec, R&R, or any other type of procedure). Changes made to
287 sections 2.6 and 3.1.

288

289 Rationale for Change

290 The study is aiming to evaluate surgical outcomes in patients whose largest preoperative angle is
291 between 15 and 50 PD. Given that the surgery window extends to 60 days after enrollment and
292 that surgery could potentially occur even later, it is possible that a patient's exotropia could
293 increase or decrease out of the eligibility range of 15 to 50 PD before surgery. As discussed in
294 protocol change #1 above, randomization to BLRrec or R&R would not be appropriate in
295 patients whose angle was greater than 50 PD. In addition, the largest preoperative angle is
296 required to be a minimum of 15 PD to ensure that a reasonable amount improvement would be
297 required to meet one of the study's treatment success criteria--an exodeviation less than 10 PD
298 by PACT at distance and near and reduction of more than 10 PD from largest of distance and
299 near angles at enrollment.

300

301 **Protocol Change #4**

302

303 Current Protocol

304 Currently the surgical dose tables start with doses for 15 PD angles.

305

306 Proposed Change

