6.1.1 Classification of Outcome

At the 3-year visit, each patient's condition will be classified as either surgical failure, success, or indeterminate as follows:

Failure = ANY of the following criteria are met at a visit 6 months or later:

1. Exotropia at distance OR near at any time during the exam (i.e., can be constant or intermittent; determined by a cover/uncover test) with a magnitude of at least 10 PD by SPCT, confirmed by a retest
2. Constant esotropia at distance OR near (determined by at least 3 cover/uncover tests—one must be before any dissociation) with a magnitude of at least 6 PD by SPCT, confirmed by a retest
3. Decrease in Preschool Randot near stereoacuity at least 2 octaves (at least 0.6 log arcsec) (*see Table 3*) from the enrollment measurement, or to nil, confirmed by a retest
4. Reoperation or treatment with botulinum toxin

Success = ALL of the following criteria are met at the 3-year visit:

1. Exodeviation less than 10 PD (tropia or phoria) by PACT at distance and near and reduction of more than 10 PD from largest of distance and near angles at enrollment
2. Esotropia less than 6 PD at distance and near by SPCT
3. No decrease in Preschool Randot stereoacuity of 2 or more octaves from the enrollment stereoacuity and no drop to nil
4. No reoperation or treatment with botulinum toxin
5. No non-surgical treatment for IXT during the study

Indeterminate = ALL of the following criteria are met at the 3-year visit:

1. Patient meets one or more of the following:

- 1439
- Exophoria ≥ 10 PD by PACT at distance or near
 - Exodeviation less than 10PD by PACT at distance and near but no reduction of more than 10 PD from largest of distance and near angles at enrollment
 - Intermittent esotropia or esophoria ≥ 6 PD at distance and/or near
- 1443 2. No decrease in Preschool Randot stereoacuity of 2 or more octaves from the enrollment stereoacuity or a drop to nil
- 1444
- 1445 3. No reoperation or treatment with botulinum toxin
- 1446

1447 **6.2 Secondary Data Analysis**

1448 All secondary analyses will be conducted on the primary cohort and stratified by IXT type.

1449

1450 **6.2.1 Subgroup Analyses**

1451 A secondary analysis will assess whether the treatment group difference in the proportion of patients with surgical failure by 3 years varies in subgroups based on baseline factors.

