- 29 • **Surgical failure at 3 years (reabeled “suboptimal surgical outcome” at 3 years)**
- 30 • **Reoperation by 3 years**
- 31 • **3-year PACT magnitude (distance and near)**
- 32 • **3-year control (distance and near)**

33

34 Not that the above variables were originally documented and created at the time of the AAPOS
35 presentation using pre-closeout data in January 2017; however, as part of the verification of the ESA 2017
36 presentation in August 2017, these variables were rerun using post-closeout data and incorporated into the
37 ROSTER dataset used for ESA. The manuscript dataset will start with ESA dataset and add additional
38 data needed for the manuscript.

39 **The current document contains the following outcomes:**

- 40 • **Exotropia failure by 3 years (using exotropia criteria of surgical failure)**
- 41 • **Constant esotropia failure outcome (using constant esotropia criteria of surgical failure)**
- 42 • **Stereoacuity failure outcome (using stereoacuity loss criteria of surgical failure)**
- 43 • **3-year stereoacuity (distance and near)**
- 44 • **Complete or near-complete resolution at 3 years without regard to previous surgical failure**
- 45 **(post hoc)**
- 46 • **Complete or near-complete resolution at 3 years with no previous surgical failure (pre-**
- 47 **specified)**
- 48 • **IXT Questionnaire (IXTQ) scores for parent, proxy and child components**
- 49 • **Additional tabulations**

50

51

52

53 **1.1 Objective**

54 To compare 3-year outcomes between patients treated with bilateral lateral rectus muscle recession (BLR)
55 versus those treated with unilateral lateral rectus recession (R/R)

56
57 **1.2 Cohort of Interest**

58 Briefly, the IXT1 study enrolled patients who were 3 to <11 years of age, had stereoacuity of 400 arcsec
59 or better, and were undergoing surgery for intermittent exotropia (N = 265 overall). The cohort of interest
60 is the primary cohort of 197 patients with basic-type IXT and with largest preoperative exodeviation
61 between 15 and 40 PD by PACT at remote distance, distance, or near (101 in BLR group, 96 in R/R
62 group).

63
64 **1.3 Cause-specific surgical failure outcomes**

65 As secondary analyses, three cause-specific suboptimal outcomes by 3 years were specified post hoc, for
66 the exotropia, constant esotropia, and stereo loss criteria defined in the primary outcome (Table 1). These
67 cause-specific outcomes differ from the primary outcome in two ways: 1) the primary outcome refers to

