1.5 Complete or Near-complete Resolution at 3 Years

Complete or near-complete resolution at 3 years was defined post hoc as meeting all of the following at the 3-year visit:

1. Exodeviation <10 PD (tropia, phoria, or no deviation) by both SPCT and PACT at distance and near and ≥ 10 PD reduction in PACT magnitude from distance and near angles at enrollment provided the corresponding angle was at ≥ 10 PD at baseline.
 - This criterion was originally written as ≥ 10 PD reduction in PACT magnitude from *largest of* distance and near angles at enrollment. After asking the protocol chairs to clarify which angle needed to be reduced by ≥ 10 PD at 3 years in cases where the distance and near angles at enrollment are the same magnitude (i.e. neither is the ‘largest’), it was decided that both angles should be reduced by ≥ 10 PD in order to meet the criterion, if the angle was at ≥ 10 PD at baseline, OR should be reduced to orthodeviation (0 PD) if the angle was at <10 PD at baseline. *Note that because all patients in the basic primary cohort have distance and near PACT ≥ 10 PD, this caveat is not cited in the manuscript as being part of the criteria. Only one patient in one of the secondary cohorts was <10 PD at baseline—a 3 PD near angle which was ortho at 3 years.* The revised criterion was extended to all patients, not only those whose enrollment PACT was the same magnitude at distance and near, for consistency. For example, if a patient with 20 PD at distance and near at baseline is required to have a reduction ≥ 10 PD at both distance and near at 3 years in order to be eligible to meet complete or near-complete resolution, then a patient with 25 PD at distance and 15 PD at near should also be required to have both reduced by ≥ 10 PD at 3 years, otherwise the first patient is being penalized simply for having the same measurement at both distances.
2. Esotropia <6 PD (tropia or no tropia, *note that phoria does not apply to SPCT*) at distance and near by SPCT
3. No decrease in Preschool Randot stereoacuity of ≥ 2 octaves from the enrollment stereoacuity or to nil
4. No reoperation or treatment with botulinum toxin
5. No non-surgical treatment for a recurrent or residual exodeviation

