Although complete or near-complete resolution was specified post hoc, a three-level failure/indeterminate/success outcome was prespecified in the protocol; the only difference between the “success” level and “complete or near-complete resolution” is that patients who met suboptimal outcome criteria at a previous visit but not at the 3-year visits were considered failures in the pre-specified outcome but could potentially be considered complete or near-complete resolutions if all other criteria were met.

127 The treatment group difference in the proportion of participants with complete or near complete resolution
128 at 3 years was compared using Barnard’s exact test and calculating a 95% CI using Farrington-Manning
129 scores. Originally the Fisher’s exact test was used, but the corresponding exact CI is calculated in a way
130 in SAS that would permit potential disagreements on statistical significance between p values of <0.05
131 and the 95% CI, whereas Barnard’s test and Farrington-Manning scores for the 95% CIs will agree on
132 statistical significance.

133
134 Note that complete or near-complete resolution *without meeting suboptimal surgical outcome at any time*
135 was also reported in the manuscript (consistent with the prespecified “success” criteria in the protocol)
136 and compared between treatment groups using similar methods.

137 138 **1.6 IXT Questionnaire (IXTQ)**

139 For the IXTQ proxy questionnaires and for each of the three parent questionnaire subscales (psychosocial,
140 functional, and surgical), mean Rasch-based QOL scores at 3 years were compared between treatment
141 groups using linear regression models adjusting for the baseline score.

142 For the IXTQ child questionnaire, because some participants were too young for the IXTQ at baseline
143 (those enrolled 3-<5 years of age) and because some children completed the 5 to 7-year old IXTQ version
144 at baseline and the 8 years and older version at 3 years, the two age versions were evaluated separately
145 and mean QOL scores at 3 years were compared between treatment groups using linear regression models
146 that did not adjust for baseline. Because the Rasch scores can be difficult to interpret, the mean of the 0 to
147 100 scores based on the Rasch scores will be cited as the mean in each treatment group.

148
149 The assumptions of ANOVA/ANCOVA will be tested and if violated, a non-parametric test such as
150 Wilcoxon rank sum test will be used.

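### The 2018 SAP names earlier-failure handling as the sole departure from protocol Success and calls its no-previous-failure outcome prespecified, but the angle rule and other criteria also changed

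*SAP*

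**What the plan says.** Protocol 6.1.1 requires for Success at 3 years, among other items, an exodeviation below 10 PD by PACT at both distances and a "reduction of more than 10 PD from largest of distance and near angles at enrollment". The April 2010 amendment, in its rationale for Protocol Change #3, gives the same threshold: "by PACT at distance and near and reduction of more than 10 PD from largest of distance and" near angles. A patient who ends below 10 PD "but no reduction of more than 10 PD from largest of distance and near angles at enrollment" is classed Indeterminate. Protocol 6.2.3 plans a comparison of the Success proportion by Fisher's exact test with a 95% confidence interval.

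The May 2018 SAP, section 1.5, defines complete or near-complete resolution and says openly that it is post hoc. Its first criterion needs a reduction of at least 10 PD at both distance and near. A note explains the move to both angles and begins "This criterion was originally written as ≥ 10 PD reduction in PACT magnitude from" the larger angle. The section then says that a three-level "failure/indeterminate/success outcome was prespecified in the protocol; the only difference between the" Success level and resolution concerns patients who had failed at an earlier visit.

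The no-previous-failure version is labelled in three places. The outcome list under Important Notes has "Complete or near-complete resolution at 3 years with no previous surgical failure (pre" followed by the rest of the word prespecified. Section 1.5 says it "was also reported in the manuscript (consistent with the prespecified" success criteria. Objective #4, step 1, has "Complete or near-complete resolution at 3 years with no previous failure (consistent with pre" and goes on to name the protocol's success criteria. Objective #4 gives this version the same values as the post hoc version, except that anyone with an earlier suboptimal outcome counts as not resolved.

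**The concern.** If resolution differs from Success only in how earlier failures are treated, then adding a bar on earlier failure should give back the protocol's Success. The SAP's label depends on that step. If other criteria changed as well, the result is a modified outcome carrying the label of the protocol's secondary outcome, and the protocol's own outcome has no objective in either SAP.

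The 2018 SAP took effect on 14 May 2018 and works from a 3-year closeout database dated 20 June 2017. A definition settled in that document needs an accurate account of what was fixed beforehand. A reader who relies on the outcome list or the one-difference sentence would not get one.

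**Working it through.** No stated figure depends on this point, so there is none to reproduce. The check sets the definitions side by side and then tests whether the two angle rules can classify the same patient differently.

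| Item | Protocol 6.1.1 Success | 2018 SAP, 1.5 and Objective #4 | Acknowledged in the SAP? |
|---|---|---|---|
| (a) Cut-off for the fall | more than 10 PD | at least 10 PD | No; 1.5 gives the original as at least 10 PD |
| (b) Angle tested | largest of distance and near | both, for all patients | Yes, with reasons, then contradicted by the one-difference sentence |
| (c) Exodeviation below 10 PD | PACT | SPCT and PACT | No |
| (d) Non-surgical treatment | none for IXT | none for recurrent or residual exodeviation; treatment for esodeviation allowed | Not as a difference from the protocol |
| (e) Baseline angle | at enrollment | randomization-form angle replaces the corresponding distance or near angle | Described, not presented as a difference |

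Because the no-previous-failure version takes its values from the post hoc version, it inherits all five rows.

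**Angle rules with one common baseline.** Let L and S be the larger and smaller baseline angles, and rL and rS the matching 3-year exodeviations, each below 10 PD.

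- Protocol: L − rL > 10.
- SAP: L − rL ≥ 10 and S − rS ≥ 10.

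Meeting the SAP rule only requires L − rL = 10. Since rL < 10, this needs L < 20. On the 2 PD prism steps described in the April 2010 amendment (Protocol Change #4), and with L at least 15, L is then 16 or 18.

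- Example: 18/18 PD to 8/8. Each fall is 18 − 8 = 10. The SAP angle rule is met; the protocol rule is not, so the patient is protocol Indeterminate.

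Meeting the protocol rule only requires S − rS < 10. Since rS < 10, this needs S < 20.

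- Example: 25/15 PD to 8/8, with the baseline the SAP itself uses. The fall from the largest angle is 25 − 8 = 17, so the protocol rule is met. The near fall is 15 − 8 = 7, so the SAP rule is not. From this baseline the protocol rule is met at any residual below 10 PD, while the SAP rule fails whenever the near residual exceeds 5 PD.
- A near angle of 16 PD, which lies on the prism steps, gives the same answer: 16 − 8 = 8.

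If both baseline angles are 20 PD or more, each fall exceeds 10 PD and both rules are met. Enumeration over assumed baseline values (20, 25, 30, 35 and 40 PD, pairs within 10 PD of each other) agreed. There was no disagreement in 1,900 combinations with residuals of 0 to 9 PD, or in 6,859 with residuals of −9 to 9 PD.

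**With baseline substitution these limits fail.** Take enrollment-visit angles of 16/14 PD (distance/near), distance remeasured at 20 PD and entered on the randomization form, and 8/4 PD at 3 years.

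- Protocol, from the enrollment visit: 16 − 8 = 8, not met.
- SAP: 20 − 8 = 12 and 14 − 4 = 10, met.
- If the remeasured angle counts as the enrollment angle, the protocol fall is also 12 and both rules are met.

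**Points the protocol leaves open.**

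- Ties: 18/18 to 8/4 meets the protocol rule if either tied angle may count (18 − 4 = 14), but not if both must (18 − 8 = 10).
- Enrollment: section 2.6 makes enrollment official when web randomization is completed, while 2.7 and 6.1 speak of an enrollment visit or exam.
- Earlier failure: 6.1.1 counts a failure at any visit from 6 months, but its Success list has no item on earlier failure, and 6.2.3 describes reoperation as what prevents a later success.

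**Whether Success is derived anywhere.** The 2017 SAP covers failure by and at 3 years, reoperation, control and PACT. The 2018 SAP covers cause-specific failure, stereoacuity, the two resolution outcomes, IXTQ and non-surgical treatment. No objective in either derives Success by the 6.1.1 criteria.

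**The case against.** Much of this is in the open. Section 1.5 calls resolution post hoc and sets out the move to both angles with its reason, a few lines above the sentence that contradicts it. A reader might infer that this change was hidden; it was not. The cut-off change is different, because the SAP attributes the altered threshold to the very criterion it says it is revising.

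A reader might also infer that the definition was shaped by the results. The documents do not support that. They give no date for the chairs' decision, only SAP dates after closeout. The one 3-year result mentioned concerns a secondary-cohort patient and a caveat that the SAP says does not apply to the analysed cohort.

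Protocol chapter 6 describes itself as a framework for a later plan, so refinement was allowed. That permits a changed definition, but not calling it the prespecified one. Nor is this only a clarification of ties: the SAP extends the rule to all patients, and its 25/15 example has no tie.

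Three limits stand:

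- Item (e) is a possible departure only, because the protocol's use of enrollment is ambiguous.
- On a narrow reading of treatment for IXT, item (d) may be largely a clarification.
- Item (c) has limited reach in the no-previous-failure version. A confirmed exotropia of 10 PD or more by SPCT is already a failure, so the added test matters only where such a reading was not confirmed by retest and PACT was below 10 PD.

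Finally, any Success analysis run now must settle points the protocol left open, so it cannot be wholly free of post hoc choices.

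**Conclusion.** The one-difference sentence is untrue and the prespecified label is not earned. The cut-off and the angles tested clearly differ from protocol 6.1.1, the SPCT requirement and treatment wording differ on their face, and the baseline source may differ. Only the move to both angles is openly disclosed as a change of criterion, and the SAP then contradicts that disclosure.

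The angle rules can reclassify patients in either direction. With no baseline substitution and residual exodeviation below 10 PD, they cannot differ when both baseline angles are 20 PD or more. With substitution that limit is not assured. The documents do not show how many of the 197 patients are affected or whether either arm gains.

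A reader might infer that Success as the protocol defines it was never analysed. The documents show only that neither SAP has an objective for it. The matter concerns the labelling and completeness of a secondary outcome; the primary analysis of failure by 3 years is unaffected. It should be corrected.

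**What to change.** In the 2018 SAP, section 1.5, replace the one-difference sentence with a full list: earlier-failure handling and items (a) to (e), with (e) described as a possible departure. Correct the note on the original criterion so that it gives the protocol's cut-off of more than 10 PD.

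Relabel the no-previous-failure version as a post hoc modification of protocol Success in the outcome list, in section 1.5 and in Objective #4.

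Add an objective that derives Success by the 6.1.1 criteria and compares the arms with the Fisher's exact test and 95% confidence interval of 6.2.3. State as post hoc clarifications the choices made on ties, on which measurement counts as the enrollment angle, and on whether an earlier failure without reoperation bars Success. Where the readings give different results, show each.

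The cost is some SAP wording and a derived Success variable (with variants for the open readings) from data already held. One more secondary result is reported, and the modified outcome loses its prespecified label.
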